19.7 Warnings and Precautions

To avoid possible complications, be sure to review warnings and precautions section of the Directions for Use Manuals.

20 Safety Reporting

20.1 Definitions and Classification

Adverse event definitions are provided in **Error! Reference source not found.**

Table 20-1: Safety Definitions

Term	Definition
Adverse Event (AE) Ref: ISO 14155-2011 Ref: MEDDEV 2.7/3 12/2010	Any untoward medical occurrence, unintended disease or injury, or any untoward clinical signs (including an abnormal laboratory finding) in subjects, users or other persons, whether or not related to the investigational medical device. NOTE 1: This includes events related to the investigational medical device or comparator. NOTE 2: This definition includes events related to the procedures involved (any procedure in the clinical investigation plan). NOTE 3: For users or other persons, this definition is restricted to events

Table 20-1: Safety Definitions

Term	Definition
	related to the investigational medical device.
Adverse Device Effect (ADE) Ref: ISO 14155-2011 Ref: MEDDEV 2.7/3 12/2010	Adverse event related to the use of an investigational medical device NOTE 1: This definition includes any adverse event resulting from insufficient or inadequate instructions for use, the deployment, the implantation, the installation, the operation, or any malfunction of the investigational medical device. NOTE 2: This definition includes any event resulting from use error or from intentional misuse of the investigational medical device.
Serious Adverse Event (SAE) Ref: ISO 14155-2011 Ref: MEDDEV 2.7/3 12/2010	Adverse event that: a) Led to death, b) Led to serious deterioration in the health of the subject, that either resulted in: a life-threatening illness or injury, or a permanent impairment of a body structure or a body function, or in-patient or prolonged hospitalization of existing hospitalization, or medical or surgical intervention to prevent life-threatening illness or injury or permanent impairment to a body structure or a body function c) Led to fetal distress, fetal death, or a congenital abnormality or birth defect. NOTE 1: Planned hospitalization for a pre-existing condition, or a procedure required by the clinical investigational plan, without serious deterioration in health, is not considered a serious adverse event.
Serious Adverse Device Effect (SADE) Ref: ISO 14155-2011 Ref: MEDDEV 2.7/3 12/2010	Adverse device effect that has resulted in any of the consequences characteristic of a serious adverse event.
Unanticipated Serious Adverse Device Effect (USADE) Ref: ISO 14155-2011 Ref: MEDDEV 2.7/3 12/2010	Serious adverse device effect which by its nature, incidence, severity, or outcome has not been identified in the current version of the risk analysis report. NOTE 1: Anticipated serious adverse device effect (ASADE) is an effect which by its nature, incidence, severity or outcome has been identified in the risk analysis report.
Device Deficiency Ref: ISO 14155-2011 Ref: MEDDEV 2.7/3 12/2010	A device deficiency is any inadequacy of a medical device with respect to its identity, quality, durability, reliability, safety or performance. NOTE 1: Device deficiencies include malfunctions, misuse or use errors, and inadequate labeling.

Underlying diseases are not reported as AEs unless there is an increase in severity or frequency during the course of the investigation. Death should not be recorded as an AE, but should only be reflected as an outcome of a specific SAE (see Table 20-1 for AE definitions).

Any AE experienced by the subject after informed consent, whether during or subsequent to the procedure, must be recorded in the eCRF.

Refer to Section 19 for the known risks associated with the device(s).

NOTES:

1. For the purposes of this study, hospitalization is defined as any in-patient admission.
2. Hospitalizations occurring for the purpose of performing a planned procedure as per routine care such as implant procedures, or follow-up visits, are not to be reported as a SAE. However, complications or adverse events that occur during the planned procedure should be reported as (S)AEs if they meet the protocol specified definitions.
3. Elective/planned hospitalization(s) need not be reported as an SAE. However, complications or adverse events that occur during an elective/planned hospitalization, should be reported as (S)AEs if they meet the protocol specified definitions.
4. In the event of subject death during the conduct of the study, efforts should be made to perform an autopsy.
5. Sensations or side effects that occur during the programming session should not be reported as AEs. However, undesired sensations or side effects caused by the final programming parameters (including active contact, pulse width, frequency, and amplitude) that persist or occur after the completion of the programming should be reported as AEs.
6. Lack of efficacy/decreased therapeutic response should not be reported as AEs. Clinical sequelae, other than pain, that occur as a result of lack of efficacy/decreased therapeutic response should be reported as AEs
7. Clinically significant worsening of the pattern of intensity or distribution of Baseline pain symptoms should be reported as an AE.
8. Device deficiencies, including, but not limited to device/lead migrations, which are not associated with an adverse clinical outcome should only be reported as device deficiencies. However, if a device deficiency precipitates an AE, the AE should be reported in the *Adverse Event* eCRF and the device deficiency should be documented in the *Device Deficiency* eCRF.

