During the course of the study, it is possible that leads may be placed incorrectly, migrate, or malfunction and require repositioning or replacement. It is also possible that the extensions or splitters or IPG may be uncomfortable or malfunction and may require repositioning or replacement. The decision to reposition or replace any device component will be made by the investigator and only if the subject agrees. Subjects not agreeing to a recommended lead revision will be withdrawn from the study but will be included in the intent-to-treat and safety analyses. Subjects agreeing to revision will continue on study and will be followed according to the original study schedule. Effectiveness data from these subjects will be included in the intent to treat analysis. Any replacements or revisions performed during the course of the study must be documented. Acute opioid pain medications may be taken per standard of care.

11.12. *Study Completion*

All subjects permanently implanted with an IPG will be followed through completion of the End of Study visit (12-months post-Activation Visit). The End of Study Action Plan (see Section 10.5) defines the actions to be taken when the subject reaches the end of their study participation.

11.13. *Source Documents*

Where copies of the original source document as well as printouts of original electronic source documents are retained, these shall be signed and dated by a member of the

investigation center team with a statement that it is a true reproduction of the original source document.

Table 11-2: Source Documentation Requirements

Requirement	Disposition
Hospital records and/or clinical and office charts including the evidence of but not limited to inclusion/exclusion criteria, informed consent, procedures, laboratory results, medications, assessment of adverse events, health resource utilization information	Retained at investigational site
Imaging films/prints documenting lead(s) location	Retained at investigational site
Assessments and questionnaires	Retained at investigational site and/or electronic data collection platform / EDC
Clinician programmer printouts/electronic files for programming information	Retained at investigational site

12. Statistical Considerations

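### Note 3 of section 20.1 exempts planned admissions from SAE reporting more widely than Table 20-1 does, so a new complication treated in a scheduled admission can be under-classified

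*Combined protocol and SAP*

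**What the plan says.** Under Table 20-1 (section 20.1), one route to an SAE is an adverse event that led to serious deterioration in health with one of several listed results. These include "in-patient or prolonged hospitalization of existing hospitalization" and, separately, "medical or surgical intervention to prevent life-threatening illness or injury or permanent impairment to a body structure or a body function". A note inside that table entry gives the exclusion: "Planned hospitalization for a pre-existing condition, or a procedure required by the clinical investigational plan, without serious deterioration in health, is not considered" an SAE.

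The numbered notes below the table then add:

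- Note 1: "For the purposes of this study, hospitalization is defined as any in-patient admission".
- Note 2: "Hospitalizations occurring for the purpose of performing a planned procedure as per routine care such as implant procedures", or for follow-up visits, are not to be reported as SAEs. Complications during the planned procedure are still reportable.
- Note 3: "Elective/planned hospitalization(s) need not be reported as an SAE". Its second sentence reads: "However, complications or adverse events that occur during an elective/planned hospitalization, should be reported as (S)AEs if they meet the protocol specified definitions".

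Section 11.11 foresees repeat surgery. Leads may migrate or malfunction, and the "extensions or splitters or IPG may be uncomfortable or malfunction and may require repositioning or replacement". The investigator decides on a revision, and it goes ahead only if the subject agrees.

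Table 20-3 asks for a USADE within 1 business day, an SAE or SADE within 2 (or as local rules require), and other adverse events in a timely manner, with 10 business days recommended. Sections 7.5 and 12.5 name the rates of related adverse events, SAEs including SADEs, and USADEs as the safety parameters.

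**The concern.** A site deciding whether an event is serious has two rules that do not agree. The exclusion in Table 20-1 depends on why the subject was admitted and on whether health had seriously deteriorated. Note 3 depends only on whether the admission was elective or planned. A complication that arises after implant and is corrected in a booked admission falls in the gap between them.

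Three things are at stake. First, an event not graded serious cannot be a SADE, and an event that is not a SADE cannot be a USADE, so one grading decision affects all three classes. Second, the study has a single arm, so the absolute rate is the safety result and no control arm would share the under-classification. Third, timing: section 22.1 relies on the sponsor's medical director evaluating events once they are reported, and section 23.4 lists late SAE reporting as a possible reason to suspend or terminate a site. Sites therefore need one rule on what counts as an SAE.

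**Working it through.** The plan gives no figure to reproduce here. The check compares the texts and adds a short illustration of scale.

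**1. The exclusions side by side**

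| | Table 20-1, note in the SAE entry | Note 2 | Note 3 |
|---|---|---|---|
| Admission covered | Planned | For a planned routine-care procedure or follow-up visit | Any elective or planned |
| Limit on reason | Pre-existing condition or plan-required procedure | Routine care, with implant as the example | None |
| Limit on severity | No serious deterioration in health | None | None |
| What is restored | Not applicable | Events during the procedure | Events during the stay |

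Note 3 lacks the limits on reason and severity. Note 2 lacks the severity limit. Its implant example largely overlaps with a plan-required procedure, but its reference to routine care could be read to include a revision.

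**2. A test case**

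Take a device or procedure complication that begins after implant, leads to serious deterioration in health and is treated in a booked in-patient admission.

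- Table 20-1: the condition is not pre-existing. A revision is not plan-required, because section 11.11 leaves it to the investigator's decision and the subject's agreement. Serious deterioration is present, which by itself defeats the exclusion. The stay is a hospitalization under Note 1. The event is an SAE.
- Note 3: the admission is planned, so it need not be reported as an SAE. The second sentence does not help, because the complication began before the stay.

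The two texts give different answers for the same event.

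**3. What changes if the site follows Note 3**

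- Classification: the event is a related adverse event, but not an SAE, SADE or USADE.
- Timing from Table 20-3: 10 − 2 = 8 business days later for an SAE or SADE, and 10 − 1 = 9 for a USADE. These are nominal differences. The 10 days are a recommendation, and the 2 days give way to local rules.

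**4. Scale**

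The cap is 60 implanted subjects (section 10.4). If k subjects have their only SAE missed, the proportion with an SAE falls by k/60:

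- k = 1: 1/60 = 1.7 percentage points
- k = 3: 3/60 = 5.0 percentage points

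The values of k are illustrative. Section 12.6.1 defines the safety set as all who sign consent. If that number exceeds 60, each missed subject lowers the rate by less.

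**The case against.** The best defence is that Note 3 exempts the hospitalization, not the adverse event. On this reading a planned stay is not an SAE in itself, while the complication behind it is graded under Table 20-1 as usual. The text gives real support for this:

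- The wording is permissive.
- Section 20.1 requires every adverse event after consent to be recorded.
- Section 17.2 and the adverse event form in Table 20-3 require seriousness to be assessed.
- The SAE and SADE definitions are not amended.
- The SAE criterion for surgical intervention does not depend on hospitalization.
- Device deficiencies, including lead migration, have their own 2-business-day report whether or not an SAE occurred.

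Much of this stands, and it limits the point. A reader might infer that such events simply drop out of the safety data. The documents do not support that: the event stays in the related adverse event rate, and only its seriousness class and timeline are at risk. A reader might also infer that every scheduled revision is a lost SAE. That does not follow either, because Table 20-1 requires serious deterioration in health. A revision for discomfort alone may not be an SAE under any of these texts.

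The defence does not remove the conflict. Seriousness must be assessed, but Notes 1 to 3 are part of the guidance that sites use to assess it. The intervention criterion is confined to preventing life-threatening illness or injury, or permanent impairment. A wound or pocket complication with a sound device need not be a device deficiency, and a deficiency report does not itself enter the SAE or SADE rate.

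**Conclusion.** The conflict is in the current text and should be reconciled. Note 3, and in part Note 2, is wider than the exclusion in Table 20-1. A post-consent complication that led to serious deterioration and was treated in a scheduled admission can therefore go unreported as an SAE, and sites may grade identical events differently. The conclusion is that such events may be under-classified and reported later, not that they will be.

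The size cannot be estimated from the documents. A reader may want to assume a percentage of subjects readmitted for revision, or to treat scheduled revision as the usual course. Section 11.11 says only that revisions are possible and gives no frequency. The 1.7 points per missed subject assumes that 60 subjects are implanted and form the denominator, that the event is that subject's only SAE, and that no other SAE criterion leads the site to report it. The wording mismatch is certain; its effect on the reported rates is not.

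**What to change.** Reconcile Notes 2 and 3 with the exclusion in Table 20-1:

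- Limit the exemption to planned admissions for a pre-existing condition or a plan-required procedure, in each case without serious deterioration in health. Name the initial screening trial and implant as plan-required, since section 11.4 has them done under each site's standard of care.
- State that an adverse event that began or worsened after consent and is the reason for an admission, scheduled or not, is assessed against all SAE criteria in Table 20-1. If serious, it is reported on the SAE or USADE timeline.
- Keep the existing sentences on complications during the procedure or stay.
- Optionally, add an eCRF field for the reason for each admission, so that grading can be checked across sites.

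The cost is new wording in two notes and, if wanted, one eCRF field. The downside is a few more SAE reports and a slightly higher stated SAE and SADE rate.

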20.2 Relationship to Study Device(s)

The Investigator must assess the relationship of the AE to the study device or procedure. See criteria in **Error! Reference source not found.**

Table 20-2: Criteria for Assessing Relationship of Study Device or Procedure to Adverse Event

Classification	Description
Unrelated	The adverse event is determined to be due to a concurrent illness or effect of another device/drug and is not related to the investigational product.
Related	d) The adverse event is determined to be potentially related to the investigational product, and an alternative etiology is equally or less likely compared to the potential relationship to investigational product, or e) There is a strong relationship to investigational product, or recurs on re-challenge, and another etiology is unlikely, or There is no other reasonable medical explanation for the event.

The Investigator must assess the potential relationship of all adverse events to the **device and procedure**. All **device** related adverse events will be assessed according to their relationship to one of the following sub-categories:

- **Device Hardware-Related AEs:** AEs that can reasonably be attributed to the mere physical presence of the device or to deficiency of the device (i.e., an allergic response to device materials).
- **Stimulation-Related AEs:** AEs that can reasonably be attributed to the effects of stimulation. A relationship to stimulation may be determined by demonstrating a predictable response to the alternating between stimulation-on and stimulation-off settings. However, a relationship to stimulation may also be reported without demonstrating a predictable response to the alternating between the stimulation-on and stimulation-off settings if in the opinion of the Investigator the AE is potentially related to stimulation.
- **Procedure Related AEs:** AEs that can reasonably be attributed to a **study protocol required procedure**.

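### Note 5 in section 20.1 excludes programming-session side effects with no exception for serious reactions or for lasting reactions to non-final settings, and it conflicts with the protocol's general AE and SAE duties

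*Combined protocol and SAP*

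**What the plan says.** Note 5 in section 20.1 has two sentences. The first is an exclusion: "Sensations or side effects that occur during the programming session should not be reported as AEs". The second is an exception to it. It covers "undesired sensations or side effects caused by the final programming parameters" and attaches a timing condition, namely those "that persist or occur after the completion of the programming should be reported as AEs".

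Other parts of the safety chapter set general duties:

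- Table 20-1 defines an AE broadly: "Any untoward medical occurrence, unintended disease or injury, or any untoward clinical signs". A note to that definition adds: "This definition includes events related to the procedures involved (any procedure in the clinical investigation plan".
- The text of section 20.1 says: "Any AE experienced by the subject after informed consent, whether during or subsequent to the procedure, must be recorded in the eCRF".
- Section 20.2 defines stimulation-related AEs as "AEs that can reasonably be attributed to the effects of stimulation". It does not limit the class to final settings.
- Section 17.2 makes the investigator report all SAEs to the sponsor. Table 20-3 in section 20.3 sets 2 business days for SAEs and 1 for USADEs. Its note has SAEs and device- or procedure-related AEs collected from consent to study end.

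Note 2 in section 20.1 also contains an exclusion, for planned hospitalizations, but it keeps a safeguard: "complications or adverse events that occur during the planned procedure should be reported as (S)AEs if they meet the protocol specified definitions". Note 3 has a parallel safeguard. Note 5 has none.

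**The concern.** Programming is where different stimulation settings are tried and where intolerance of a setting is most likely to show. A setting dropped because the subject reacted badly to it is, by that fact, not a final setting. On a plain reading of Note 5, the effects of such settings fall under the exclusion and outside the exception.

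The safety parameters in sections 7.5 and 12.5 are rates of device- and procedure-related AEs and of SAEs. If some sites apply Note 5 and others apply the general recording duty, ascertainment will differ across up to 10 sites, and any omissions lower the rate. The study is single-arm (section 8), so no comparator collected under the same rule offsets an under-count. The sponsor's safety evaluation in section 22.1 starts when an event is reported, so an event withheld under Note 5 would not reach it by that route.

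**Working it through.** The plan states no figure on this point, so the check is textual. The inputs are the two sentences of Note 5, Notes 2 and 3, Tables 20-1 and 20-3, and sections 17.2, 20.1 and 20.2.

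**Step 1: the conditions in Note 5.** The exclusion has one condition: the effect occurs during the session. Nothing limits it by seriousness or duration. The exception has two conditions that must both hold: the effect is caused by the final parameters, and it persists or occurs after programming.

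**Step 2: four cases set against Note 5 and the general duties.**

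| Case | Note 5 | General duties |
|---|---|---|
| (a) Transient, non-serious effect of a tested setting, gone before the session ends | Not reported | Arguably an AE under the broad definition |
| (b) Effect of a tested, non-final setting that begins in the session and outlasts it | Began in the session, and the exception fails on cause | Recorded as an AE after consent; fits the stimulation-related class |
| (c) Serious effect during the session | Excluded unless the exception applies; no seriousness clause | Reported as an SAE under section 17.2 and Table 20-3 |
| (d) Effect of the final settings that persists or arises afterwards | Reported | Reported |

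In (d) the two agree. In (a) the exclusion is a sensible convention. The conflict that matters is in (b) and (c).

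**Step 3: does any text resolve the conflict?** Sections 7.5, 11.5, 20.1 to 20.5 and 22.1 and Table 20-3 contain no statement that Note 5 yields to the general duties, or the reverse. Case (c) has a further difficulty: Table 20-1 defines an SAE as a kind of adverse event, so a site told not to report something as an AE may conclude that there is no SAE to report.

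**Step 4: how often Note 5 can apply.** Table 11-1 marks programming as required at Activation and optional at the Programming, 3-, 6- and 12-Month Visits, although section 11.6 describes programming at the Programming Visit as something that will happen. With 60 implanted subjects, required sessions by the table are 1 × 60 = 60, and scheduled opportunities are at most 5 × 60 = 300. Sections 11.5 and 11.10 allow further visits without a cap. Table 26-1 defines programming to include the external trial stimulator, and section 11.4 allows programming at implant, so Note 5 can reach those occasions too. These are counts of opportunities. Turning them into missed events would need a per-session reaction rate, which the documents do not give.

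**The case against.** The strongest case against has four parts.

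1. Note 5 does not contain the word only. An effect still present after the session is arguably no longer confined to it, so the general recording duty would cover case (b).
2. Note 5 speaks of sensations and side effects, whereas Notes 2 and 3 speak of complications and (S)AEs. It can be read as aimed at the expected sensations of testing settings and not at events of SAE grade. The SAE duties in section 17.2 and Table 20-3 carry no programming exception.
3. There are other routes to capture. Table 11-1 requires AE collection at every visit, subjects are asked about events since their last visit, and section 20.3 has them told to contact their physician at once about any event.
4. Leaving momentary sensations unrecorded while settings are adjusted is a deliberate and reasonable choice.

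Much of this stands. A reader might infer from Note 5 that a serious or lasting reaction to a tested setting will not be reported and that the sponsor will never see it. The documents do not support that. Separate duties require such events to be recorded, and a site could well follow them. The fourth part stands in full, and the fix keeps that convention.

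What does not stand is the suggestion that there is no conflict. The second sentence of Note 5 uses the same words, sensations or side effects, for events that are to be reported as AEs, so the term is not confined to trivial sensations. The reading in the first part is possible, but the text does not state it. The other routes bring an event to the site's attention; the site must still decide whether Note 5 bars it from being reported.

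**Conclusion.** Note 5 conflicts with the AE definition, the general recording duty, the stimulation-related class and the SAE duties, and the protocol does not say which governs. The conflict concerns serious in-session reactions and lasting reactions to tested, non-final settings. The risk is inconsistent under-reporting between sites, which would bias the device-related AE rate downward. Certain loss of events is not shown.

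The direction assumes that at least some such reactions occur and that at least some sites follow Note 5 in preference to the general duties. If either fails, the effect is nil. A reader might be tempted to put a count or percentage on the missing events, but any such figure would rest entirely on an assumed per-session rate with no basis in the documents. The point concerns the safety rates and does not touch the 3-month responder analysis. It merits correction because a stated rule, not just missing detail, produces the conflict, and the correction is cheap.

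**What to change.** Reconcile Note 5 with Tables 20-1 and 20-3 and sections 17.2, 20.1 and 20.2, using the safeguard already in Notes 2 and 3. That safeguard alone would nearly cancel the exclusion, because almost any unpleasant sensation meets the broad AE definition, so the exclusion itself also needs a limit. Suggested wording:

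*Transient, non-serious sensations that resolve within the programming session are not reported as AEs. Any sensation or side effect that meets the SAE definition, or that persists after the session, is reported, whichever tested or final setting caused it. Effects of the final settings that arise after the session are reported as before.*

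Count these events in the stimulation-related class, and carry the same wording into the eCRF instructions so that all sites apply one rule. The change affects only what is recorded; it alters no programming or treatment rule.

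The cost is two or three sentences of protocol text, with amendment approval under section 14 if the change is judged to affect safety or data integrity, plus a few more AE forms. The stimulation-related AE rate may look slightly less favourable.
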